7.5. Method of Treatment Assignment

Participants will be randomized in a 1:1 ratio to HCQ or ascorbic acid at the level of the household (all eligible participants in 1 household will receive the same intervention). The randomization plan will be written by the Study Statistician.

The randomization code and resulting allocation list will be generated and maintained by the Study Statistician. The list will be blocked and stratified by site and contact type (household versus healthcare worker).

7.6. Blinding

This is a blinded study. Eligible participants will receive one of the following therapies:

- HCQ 400 mg orally daily for 3 days then 200 mg orally daily for an additional 11 days
- Ascorbic acid 500 mg orally daily for 3 days then 250 mg orally daily for 11 days

HCQ and ascorbic acid will appear similar, and taste will be partially masked as HCQ can be bitter and ascorbic acid will be sour.

The participants will be blinded to their randomization group once assigned. Within 24 to 48 hours of enrollment, the unblinded Study Pharmacist will use the randomization code revealed at the point of randomization to provide the participant with their group assignment and dispense the allocated study medication in a bottle marked with the study label. The medication and medication information, mid-nasal swabs sufficient to complete the study procedures, *DBS sampling kit, if within the sub-study*, and study instructions will be delivered to the participant.

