3.2.5. Rationale for Ascorbic Acid Control as a Comparator

In healthy adults, COVID-19 infection is likely to express as a febrile disease with cough and fatigue, but variability in symptomatology (to include oligosymptomatic infection) is a possibility [28]. Study participants will have already been exposed to SARS-CoV-2, likely with quarantine as a result, so randomization is unlikely to affect future risk behavior with respect to SARS-CoV-2. Symptom reporting may vary based on participants' perception as to whether they are taking HCQ or ascorbic acid [29], but the primary study endpoints of infection and viral shedding are not affected.

Therefore, use of a control is acceptable and ethical both for participants' health and safety as well as ensuring the most rigorous trial design to evaluate PEP for SARS-CoV-2. Participants will be blinded to their allocation to the extent possible, with a comparator of ascorbic acid used to provide a similar taste as HCQ. Specifically, tablets will not be labeled as either HCQ or ascorbic acid, and an ascorbic acid tablet that is comparable in size and shape to HCQ will be used. All participants from the same household will be assigned the same regimen, so that comparisons cannot be made between the medications and to minimize crossover through drug sharing by household members.

The dose of ascorbic acid (500 mg for 3 days, then 250 mg daily for 11 days) is safe. All participants, regardless of assigned group, will be able to take additional ascorbic acid (e.g., over the counter vitamins, or through food) should they choose, as there is no known maximum daily safe dose of ascorbic acid. Clinical trial evidence has demonstrated that ascorbic acid, alone or in combination with other micronutrients, does not substantially reduce the risk of upper respiratory infections or severe consequences of infectious processes [30,31]; thus, ascorbic acid is not expected to have a prevention effect for SARS-CoV-19 and is considered a placebo-equivalent product for this study [32].

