Packaging and Labeling	The medication for home delivery will be dispensed in an unmarked container with the study label. The container will be labeled with a unique identifier. The container will be packed in a standard box used for mail delivery of medications as needed.	
Manufacturer	To be determined	To be determined

7.2. *Risks to the Participants*

7.2.1. *Risks Associated with PEP Administration with HCQ*

The risks associated with PEP reflect the adverse events (AEs) related to HCQ administration. With tens of millions of doses administered for malaria and autoimmune diseases, the side effect profile of HCQ is well described and the drug is generally well tolerated. With short-term administration (as opposed to chronic/year-long use in rheumatologic disease management), the major AEs are gastrointestinal (nausea, vomiting, dyspepsia, abdominal cramps, and diarrhea) and transient skin rashes. The gastrointestinal symptoms may vary by specific generic manufacturer of HCQ [35] and are best managed by taking the drug with food or a glass of milk (Appendix 6). A transient rash, most commonly morbilliform or psoriasiform, can develop in 10% of participants, often with a sustained loading dose, and is often managed by lowering the dose. To avoid this potential side effect, this protocol is using a short loading dose, not a sustained one. Uncommonly, idiosyncratic leukopenia/thrombocytopenia can occur and the drug

should not be given to those with underlying bone marrow disorders. Lastly, hypoglycemia can occur and those taking insulin or glucose-lowering drugs are at risk; blood glucose should be monitored.

Minor blurry vision may occur with acute HCQ use, is reversible, dose-related, and is generally not severe. It may also be associated with mild headaches. It is caused by deposition of HCQ in the cornea or ocular muscle weakness, and is not a predictor of long-term toxicity. Participants experiencing minor blurry vision may adjust to it with counselling and reassurance that it is reversible and not progressive.

More severe rashes, including drug-related eosinophilia with systemic symptoms and Stevens-Johnson syndrome occur rarely.

Long-term manifestations of HCQ, including retinitis, renal and hepatic disease, and cardiomyopathy ([Appendix 4](#)), are not likely in this 2-week PEP exposure.

7.2.2. *Risks Associated with COVID-19 Surveillance and Quarantine*

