- Participants who develop a Grade 3 symptomatic toxicity thought by the site Investigator to be related to study drug should have HCQ PEP withheld, and the site should consult with the Core Protocol team. The participant should be reevaluated every 2 days until the AE returns to Grade ≤ 2 , at which time study drug may be reintroduced at the discretion of the site Investigator in consultation with the protocol team.
- Participants experiencing Grade 3 toxicity requiring permanent discontinuation of study medication should be followed up weekly until resolution of the toxicity. Participants will have premature study treatment discontinuation evaluations performed. These participants will remain on study, off study treatment, and have all evaluations performed per the SoA.

Grade 4

- Participants who develop a Grade 4 symptomatic toxicity will have study medication permanently discontinued, and the site should notify study team within 48 hours.
- Participants experiencing Grade 4 toxicity requiring permanent discontinuation of HCQ PEP should be followed up weekly until resolution of the AE or return to baseline. These participants will remain on study, off study treatment, and have all evaluations performed per the SoA.

Specific Management of Toxicities Related to Study-Provided Drugs

Gastrointestinal disturbance

Gastrointestinal disturbance (nausea, vomiting, diarrhea) is a common known possible side effect of HCQ. Dividing doses by 6 hours and taking with food or milk may improve tolerability.

Visual disturbances

Suspected visual changes should be evaluated for possible etiologies. Participants experiencing Grade 1 or Grade 2 vision changes may continue use, at the discretion of the site Investigator. Participants who develop a Grade 3 symptomatic toxicity thought by the site Investigator to be related to study drug should have HCQ PEP withheld, and the site should consult with the Core Protocol team. The participant should be reevaluated every 2 days until the AE returns to Grade ≤ 2 , at which time study drug may be reintroduced at the discretion of the site Investigator in consultation with the protocol team.

Allergic reactions

HCQ should be discontinued permanently if a serious allergic reaction is suspected. These participants will remain on study, off study treatment, and have all evaluations performed per the standard operating procedure(s).

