2.3. RANDOMIZATION

Enrolled contacts were randomized 1:1 to receive either HCQ or ascorbic acid. Randomization tables were stratified by study site and contact type (household/social exposure or healthcare worker exposure) and blocked into groups of randomly varying size. The tables were programmed in R and allocation was performed via REDCap by site pharmacists or their designees. All other study staff were blinded to randomization group apart from the coordinating center's unblinded statistical team.

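### Protocol 7.6 says participants are blinded, then in the next sentence has the unblinded pharmacist give them their group assignment; the wording needs correcting

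*Protocol*

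**What the plan says.** Protocol 7.6 describes the study as blinded and says: "The participants will be blinded to their randomization group once assigned". The next sentence covers what happens in the 24 to 48 hours after enrollment: "the unblinded Study Pharmacist will use the randomization code revealed at the point of randomization to provide the participant with their group assignment". A second action follows in that same sentence, namely supplying the drug in a bottle that carries only the study label.

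Other sections bear on the same step:

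- Protocol 3.2.5: "Participants will be blinded to their allocation to the extent possible". It adds that "tablets will not be labeled as either HCQ or ascorbic acid", that the ascorbic acid tablet is matched to HCQ in size and shape, and that a whole household receives one regimen, partly so that members cannot compare products.
- Protocol 7.1, packaging row: "The medication for home delivery will be dispensed in an unmarked container with the study label". The container also carries a unique identifier.
- SAP 2.3: site pharmacists or their designees performed allocation through REDCap. "All other study staff were blinded to randomization group apart from the coordinating center's unblinded statistical team".

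**The concern.** The sentence in 7.6 is the operating instruction for the person who holds the code. It has two verbs. The pharmacist is to provide something to the participant, and is to dispense. The participant is the named recipient of the first, and what is provided is the group assignment. Dispensing is dealt with separately, so the first action is not simply another word for handing over the bottle. Nothing limits the group assignment to a masked code or kit number.

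At stake is the blind for outcomes that pass through the participant's own judgement or behaviour. Protocol 3.2.5 itself accepts that symptom reporting may change with what participants believe they are taking. The protocol is also offered as a model for other institutions (Protocol 11.3.6), so an error in an operating sentence could be copied.

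**Working it through.** No arithmetic applies. The check is whether the statements can all be carried out together, and which outcomes depend on the answer.

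**Step 1. The two sentences in 7.6.** The first requires that participants not know their group after assignment. The second, read as written, requires the pharmacist to tell them. It names the participant without subset or exception, so a literal reading covers everyone enrolled: up to 2000 under the protocol, including the 1240 baseline-negative participants planned in SAP 2.4.

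**Step 2. Does any other text correct the instruction?**

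| Place | What it establishes | Does it forbid disclosure? |
|---|---|---|
| Protocol 3.2.5 | Blinding intended; tablets unlabelled and matched; one regimen per household | No |
| Protocol 7.1 | Container unmarked apart from the study label and an identifier | No |
| Protocol 7.6, second half of the same sentence | Bottle carries only the study label | No |
| SAP 2.3 | Pharmacists allocate; staff other than pharmacists and the unblinded statistical team are blinded | No; participants are not mentioned |

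Every row points to an intention to blind. None tells the pharmacist to withhold the assignment.

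**Step 3. Which outcomes would be exposed if the step were followed literally?**

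- *Adverse events.* Under Protocol 10.2, a non-serious event is recorded when the participant or the clinician judges it to be associated with study medication. The participant's belief about the arm enters directly.
- *Adherence.* SAP 5.2 summarises self-reported pill taking.
- *COVID-19 diagnosis.* In SAP 7.1.2 this endpoint needs PCR confirmation, but it is defined by symptoms and dated by their onset.
- *Primary endpoint, in part.* SAP 7.1.1 counts COVID-19 confirmed by outside evaluation in the first 13 days. Under Protocol 9.1.5, outside testing begins with the participant contacting a provider. The exposure here is smaller, because the diagnosis must be confirmed and doubtful endpoints go to a blinded adjudication committee.
- *PCR results from study swabs.* Protocol 3.2.5 says the infection and shedding endpoints are not affected by perceived allocation. That is a fair limit for the swab result itself. It does not address the external diagnoses, which the protocol's swab-based primary endpoint (Protocol 4) does not mention and SAP 7.1.1 counts.

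**Step 4. Timing.** SAP 2.3 describes randomization and allocation in the past tense, so some participants may already have been through this step. Rewording the protocol cannot show what they were told.

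**The case against.** The strongest reply is that the disclosure reading goes against the rest of the plan. The study is called blinded throughout, the tablets and containers are masked, households are kept on one regimen partly to prevent comparison, and calling the pharmacist unblinded implies that others are not. Telling participants their arm would also put staff blinding at risk, since staff contact them repeatedly. The author probably meant that the pharmacist uses the code to allocate and dispense. This stands as an account of intent. It does not change what the sentence tells a pharmacist to do.

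Four stronger readings are tempting, and the documents support none of them:

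- *Participants were unmasked, or sites ran different trials.* Nothing shows that any pharmacist disclosed an arm or that sites read the sentence differently.
- *Control participants would seek HCQ elsewhere or stop swabbing.* This is speculation. Eligibility requires no plan to take additional HCQ (Protocol 6.1.1), and the daily survey asks about concomitant medication and swab adherence (Protocol 2).
- *The toxicity rules in Protocol 7.4 also break the blind, because they name HCQ.* A reader might infer this from wording such as "should have HCQ PEP withheld, and the site should consult with the Core Protocol team". But the triggers are toxicity grade, judged relatedness or a suspected serious allergic reaction, never the arm. The section uses HCQ PEP, study drug and study medication interchangeably, so a blinded site can act on masked tablets.
- *The medication information sent with the kit reveals the arm.* The protocol does not say that it differs by arm. The inference rests on silence.

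**Conclusion.** The contradiction in Protocol 7.6 is real, and no other text resolves it. It is a wording error in an operating step. The design choice, a blinded trial, is clear.

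Its potential reach is every participant if the sentence is followed literally. Its actual effect is unknown and may be nil. The size of any bias cannot be derived from the documents. If disclosure occurred, participant-attributed adverse events, self-reported adherence and the symptom-defined COVID-19 endpoint would be the most exposed. External diagnoses within the primary endpoint would be exposed to a lesser degree. On the protocol's own statement in 3.2.5, the PCR infection and shedding results would not be affected.

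This conclusion assumes that the sentence is read in its ordinary sense and that no pharmacy instruction outside these two documents already prohibits disclosure.

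**What to change.** In Protocol 7.6, replace the purpose clause, from the words about providing the group assignment through to dispensing the medication, with: *to select and dispense the allocated study medication under its unique identifier, without disclosing the group to the participant, household members or blinded staff*. The container identifier already exists in Protocol 7.1, so no new procedure is needed.

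Because allocation had begun when the SAP was written, obtain and file confirmation from each site pharmacist or designee that the arm was not disclosed to participants already randomized.

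The cost is one protocol sentence and a short documented check at each site. Sample size, alpha and the analysis models do not change.

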7.7. Preparation/Handling/Storage/Accountability

Drugs should be stored at room temperature, as per package insert. Records must be maintained that document receipt, release for dosing, disposal, or return to the sponsor.

7.8. Treatment Compliance

The participant will be contacted to ensure that they received the box of study supplies; were able to collect the first mid-nasal swab and store it appropriately; and took their first day of medication. Participants will be asked to complete a Survey that includes information regarding treatment administration. *In a sub-study, HCQ concentration via a DBS will also be evaluated.*

Consultation via Telehealth, text messaging, or telephone will be available to provide support to the participant to complete study procedures.

7.9. Concomitant Therapy

Participants will be asked about concomitant medications at the screening/baseline evaluation visit. During the study, participants will be asked to complete Surveys (Daily Survey and Exit Contact Survey) that include information regarding any medication or vaccine (including over-the-counter or prescription medicines, vitamins, and/or herbal supplements) that the participant receives during the study. At each contact, the Investigator or designee should question the participant about any medication taken.

7.9.1. Prohibited Medications

Prohibited medications include digoxin, cyclosporin, cimetidine, amiodarone, tamoxifen, and antimalarial medications (including chloroquine, artemether, lumefantrine, mefloquine).

7.9.2. Precautionary Medications

Use of medications classified as precautionary is not study prohibitory but will be discussed with the study clinician and the participant. These medications include androgens, antidiabetic agents, phenothiazines, beta-blockers, cardiac glycosides, citalopram, dapsone, escitalopram, haloperidol, herbs, maitake, monoamine oxidase inhibitors, pegvisomant, prothionamide, quinolones, salicylates, and selective serotonin reuptake inhibitors.

7.10. Treatment After the End of the Study

No additional treatment will be provided at the end of the study.

8. Discontinuation/Withdrawal Criteria

8.1. Discontinuation of Study Treatment

Study treatment will be discontinued for the following reasons:

- Requirement for prohibited concomitant medications or other contraindication to HCQ
- Occurrence of an AE requiring discontinuation of study medication
- Request by participant to terminate study treatment
- Clinical reasons believed to be life-threatening by the physician, even if not addressed in [Section 7.2](#)

Participants who stop study treatment should continue study participation off study medication with continued evaluations as per the SoA. The reason for study medication discontinuation should be recorded.

Participants who are identified as SARS-CoV-2 positive by PCR at baseline should continue study therapy and study participation.

Participants with a clinical diagnosis of COVID-19 should continue on study therapy unless they are started on COVID-19 treatment outside of the study.

8.2. *Withdrawal from the Study*

- A participant may withdraw from the study at any time at his/her own request or may be withdrawn at any time for the following reasons:
 - At the request of the primary care provider if he/she thinks the study is no longer in the best interest of the participant
 - Participant is judged by the Investigator to be at significant risk of failing to comply with the provisions of the protocol as to cause harm to self or seriously interfere with the validity of the study results
 - At the discretion of the Institutional Review Board/Ethics Committee or government agencies as part of their duties, Investigator, or industry supporter
- If the participant withdraws consent for disclosure of future information, the sponsor may retain and continue to use any data collected before such withdrawal of consent.
- If a participant withdraws from the study, he/she may request destruction of any samples taken and not tested, and the Investigator must document this in the site study records.
- See SoA for data to be collected at the time of study discontinuation and follow-up and for any further evaluations that need to be completed.

8.3. *Lost to Follow-up*

A participant will be considered lost to follow-up if he/she is unable to be contacted by the study site.

The following actions must be taken if a participant fails to comply with required study procedures:

- The site must attempt to contact the participant as soon as possible and counsel the participant on the importance of maintaining the assigned procedure schedule and ascertain whether or not the participant wishes to and/or should continue in the study.
- Before a participant is deemed lost to follow-up, the Investigator or designee must make every effort to regain contact with the participant (where possible, 3 telephone calls and, if necessary, a certified letter to the participant's last known mailing address or local equivalent methods). These contact attempts should be documented in the participant's medical record.
- Should the participant continue to be unreachable, he/she will be considered to have withdrawn from the study with a primary reason of lost to follow-up.

9. *Study Encounters*

The current COVID-19 pandemic has placed a significant burden on the healthcare system. For this study, specimen and data collection will be conducted to minimize impact of non-ill participants within the healthcare system. If the participant is assessed as eligible, contact between study participants and study personnel will occur via a Health Insurance Portability and Accountability Act (HIPAA)-compliant video conference (Telehealth), although in-person visits either at the participant's home or at a research center are permitted.

Participants will be instructed to seek clinical care should they manifest any signs or symptoms of COVID-19.

9.1. Close Contact Participants

9.1.1. Screening/Baseline Evaluation: Day 0/1

Participants will be assessed for study eligibility through a screening conducted through a web-based screening tool, HIPAA-compliant video conference (Telehealth), telephone, or text messaging.

Day 0 evaluations are as follows:

- Informed consent
- Collection of demographic information
- Collection of past and current medical conditions, including known pregnancy and/or lactation status
- Collection of concomitant medication information
- Collection of information regarding exposure to the index case
- Check of inclusion and exclusion criteria

Eligible participants will be randomized with all members of a household assigned to the same arm. Participants will receive a swab kit either via courier or mail, which includes a Quick Start Instruction Card, swabs, plastic tubes for swab collection, and a return box with affixed Category B UN3373 label, as required by International Air Transport Association (IATA) guidelines [36].

The participant will do the following on Day 1:

- Collect mid-nasal swab for PCR
- Take study therapy (HCQ or ascorbic acid, as assigned)
- Complete Daily Survey (online, Telehealth, telephone, or text messaging). This Survey will include confirmation of adherence to study therapy dosing and daily swab collection, concomitant medication review, and symptoms review.
- *If in DBS Sub-study, collect DBS samples for analysis of anti-SARS-CoV-2 antibodies (if possible).*

Instructions for skin puncture and DBS sample preparation are provided in [Appendix 6](#). A study team member will be available via Telehealth, telephone, or text messaging to provide support for completion of this study procedure.

Screening/Day 0 and Day 1 procedures may occur on the same day.

The index case SARS-CoV-2 positive test results will be confirmed through self-report of the contact participant. *If in the index case sub-study, shedding of SARS-CoV-2 will be assessed by PCR of a mid-nasal swab ([Section 9.2](#)).*

9.1.2. Day 2 Through Day 13

The participant will do the following every day from Day 1 through Day 13, inclusive:

- Collect mid-nasal swab for PCR
- Take study therapy (HCQ or ascorbic acid, as assigned)
- Complete Daily Survey (online, telephone, or text messaging). This Survey will include confirmation of adherence to study therapy dosing and daily swab collection, concomitant medication review, and symptoms review.
- *If in DBS Sub-study, collect DBS samples for analysis of HCQ concentration at any time during this period (1 to 5 times) after study drug dosing has commenced. No more than 1 sample per day should be collected.*

A study team member will be available via Telehealth, text messaging, or telephone to provide support for completion of study procedures. The courier will collect the swabs at minimum within 1 or 2 days of Day 7 and Day 13 and potentially as frequently as daily.

9.1.3. Day 14

The participant will do the following on Day 14:

- Collect mid-nasal swab for PCR
- Take study therapy (HCQ or ascorbic acid, as assigned)
- Complete Daily Survey (online, telephone, or text messaging). This Survey will include confirmation of adherence to study therapy dosing and daily swab collection, concomitant medication review, and symptoms review.
- *If in DBS Sub-study, collect DBS samples for analysis of HCQ concentration, if not already collected.*

A study team member will be available via Telehealth, text messaging, or telephone to provide support for completion of study procedures.

Participants are instructed to place their self-collected nasal swabs directly into the plastic tube that is pre-labeled with a unique barcode. Next, participants are instructed to place the plastic tube containing the self-collected nasal swab into a specimen bag, pre-packaged with an absorbent sheet, and then place the specimen bag into the provided return shipping box. Category B UN3373 stickers are affixed to the outside of the return box. Previous testing has demonstrated that respiratory viral ribonucleic acid (RNA) is stable in room temperature for up to 1 week. The courier will collect the swabs at minimum within 1 or 2 days of Day 14.

